2 STUDY OBJECTIVES

2.1 Primary objective

To assess the efficacy, as determined by the objective response rate (ORR), of INCMGA00012 in patients with unresectable locally advanced or metastatic PSqCC.

2.2 Secondary Objectives

- To assess the efficacy, as determined by the clinical benefit rate (CBR), PFS, 6-month PFS, duration of response (DoR), time to response (TTR), OS, and maximum tumor shrinkage, of INCMGA00012 in these patients.
- To evaluate the safety and tolerability of INCMGA00012 in these patients.

2.3 Exploratory Objectives

- To determine the efficacy –as determined by the ORR, CBR, and 6-month PFS based on immune-related RECIST (irRECIST).
- To evaluate predictive or prognostic, tumor- and/or immune-related biomarkers associated with disease activity status or response to treatment.
- To identify possible mechanisms of resistance to study treatments through the comparative analysis of potential biomarkers from paired pre-treatment and post-progression tumor and/or blood samples.
- To assess impact of INCMGA00012 on HIV control in participants who are known to be HIV-positive.

3 DEFINITION OF ENDPOINTS

3.1 Primary Endpoint

- The primary efficacy endpoint for the present study is the ORR.

3.2 Secondary Endpoints

- The secondary efficacy variables are CBR, DoR, TTR, PFS, OS and maximum tumor shrinkage by investigator RECIST response.

3.3 Safety Endpoints

- The safety and tolerability will be evaluated by incidence of AEs, incidence of prespecified AEs, change from baseline in targeted vital signs, and change from baseline in targeted clinical laboratory test results.

3.4 Exploratory Endpoints

- ORR, CBR, and 6-month PFS as per irRECIST.
- Relationship between tumor- and/or immune-related biomarkers, and efficacy in tumor tissue and/or liquid biopsy.

- Changes from baseline in the CD4-positive cell count and HIV viral load in participants who are known to be HIV-positive.

4 ANALYSIS SETS

The following sets will be analyzed:

- **Screening:** Patients who were present at the screening visit.
- **Safety and FAS (Full Analysis Set) Set:** patients who receive at least one dose of study medication.

Efficacy and Safety endpoints will be analyzed on the Safety/FAS set.

FAS set will be considered the primary population for the analysis.

- **Per-protocol (PP) set:** All patients that accomplish selection criteria, receive at least one drug exposure, and receive the protocol required study drug exposure and processing. Criteria for determining the “per protocol” (PP) group assignment would be established by the Steering Committee before the statistical analysis begins. This analysis will only occur if this set differs by $\geq 10\%$ from the FAS set.

The primary and secondary efficacy analyses will be performed on the FAS and PP sets.

- **Exploratory Set:** All patients with biomarker evaluable samples with the assay and alternative platforms that accomplish selection criteria and receive at least one drug exposure.

Exploratory analysis will be performed on exploratory set. A separate analysis report for such assessments will be written.

5 STATISTICAL METHODS

5.1 General Methodology

The statistical analysis will be conducted following the principles as specified in International Conference on Harmonization (ICH) Topic E9 (CPMP/ICH/363/96). The significance level will be $\alpha=0.05$ for all tests. As an exploratory study, multiple testing without adjustment of the significance level is considered acceptable.

Definition of baseline: For each safety or efficacy parameter, the last valid assessment made before first study drug administration will be used as the baseline for all analyses of that safety or efficacy parameter unless otherwise specified.

Continuous data will be summarized in terms of the number of observations, mean, standard deviation (SD), median, minimum, maximum, and first and third quartiles, unless otherwise stated. Where data are collected over time, both the observed data and change from baseline will be summarized at each time point.

The minimum and maximum will be reported to the same number of decimal places as the raw data recorded in the database. The mean, median, and first and third quartiles will be reported to one more decimal place than the raw data recorded in the database. The SD will be reported to two more decimal places than the raw data recorded in the database. In general, the maximum number of decimal places reported shall be four for any summary statistic.

Categorical data will be summarized in terms of the number of subjects providing data at the relevant time point (n), frequency counts and percentages. Changes from baseline in categorical data will be summarized using shift tables where appropriate.

Percentages will be presented to one decimal place. A percentage of 100% will be reported as 100%. Percentages will not be presented for zero counts. Unless otherwise stated, percentages will be calculated using n as the denominator, for frequency tables not assessed by time point the set will be used as denominator. If sample sizes are small, the data displays will show the percentages, but any textual report (e.g., clinical study report) will describe frequencies only.

P-values greater than or equal to 0.001, in general, will be presented to three decimal places. However, if a P-value is only presented to four decimal places (by SAS) it will not be rounded again but will be presented to four decimal places. P-values less than 0.0001 will be presented as "<0.0001".

Confidence intervals will be presented to one more decimal place than the raw data. A two-sided significance level of 5% will be used for confidence intervals.

For binary endpoints, the 95% confidence intervals (CIs) will be constructed based on an exact binary distribution.

The Kaplan-Meier method will be used to estimate the time to event function, the median of time to event and the 95% confidence interval of the same will be calculated. These confidence intervals will be calculated based on the Greenwood method. Number and proportion of events, median survival time and survival rates, with corresponding 95%CI will be calculated.

All scores and change from baseline will be summarized in terms of the number of observations, mean, standard deviation, 95%CI of mean, median, range and interquartile range. We will examine the residuals to assess model assumptions.

All report outputs will be produced using SAS® version 9.4 version in a secure and validated environment. All report outputs will be provided to the Sponsor in a single Microsoft Word document.

5.2 Subject Disposition

Descriptive statistics will be provided for the following:

- Overall number of subjects in the screening set, the number of patients eligible to participate in the study, and number of screen failures.
- Number and percent of subjects in each of the analysis sets.
- Number and percent of subjects excluded from each of the analysis sets along with reason for exclusion.
- Listing of subjects excluded from each of the analysis sets along with reason for exclusion.
- Listing of protocol deviations.
- Study termination:
 - o Number and percent of subjects who completed the study.
 - o Frequency of premature termination reasons.
 - o Listing of all dropouts along with reason for termination, treatment group and time of termination.
- Follow-up time (months), defined as the time from start dose until the last available follow-up date.
- Follow-up Dates:
 - o Database cut-off date.
 - o Start date of treatment dose of the first patient.
 - o Start date of treatment dose of the last patient.
 - o End date of treatment dose of the last patient.
 - o End date of follow-up of the last patient.

No statistical tests are planned for these data.

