
Statistics:
	
The sample size calculation is based on an exact binomial test. The clinical trial is designed to demonstrate an ORR of at least 25% and

	
to exclude a rate of less than 5% ($p_0=0.05$, $p_1=0.25$, $\alpha =0.05$, $\beta=0.80$, A'hern's exact design). At least 3 responders (18.8%) among 16 evaluable patients will be adequate to justify the investigation of this strategy in further clinical trials. Considering a drop-out rate of 10%, a sample size of 18 patients will be needed to attain 80% power at nominal level of one-sided alpha of 0.05.
 
The full analysis set will be considered the primary population for the analysis.

Study Periods
	
Recruitment period:
 
Estimated at least 12 months in order to enroll 18 patients.
 
End of study:
 
EoS will occur 12 months after the last patient has been enrolled in the study (treatment start).

V. TABLE OF ABBREVIATIONS

Definition	Abbreviation
AE	Adverse event
ALK	Alkaline phosphatase
ALP	Alkaline phosphatase
ALT	Alanine aminotransferase
ANC	Absolute neutrophil count
aPTT	Activated Partial Thromboplastin Time
AST	Aspartate aminotransferase
BCG	Bacillus Calmette–Guérin
CBR	Clinical benefit rate
CI	Confidence interval
CNS	Central Nervous System
CR	Complete response
CRF	Case report form
CRO	Clinical Research Organization
DEHP	(2-ethylhexyl) phthalate
DNA	Deoxyribonucleic acid
DoR	Duration of response
EC	Ethics Committee
ECI	Event of clinical interest
ECOG	Eastern Cooperative Oncology Group
EGFR	Epidermal Growth Factor Receptor
EMA	European Medicines Agency
EoS	End of study
EoT	End of treatment
ESA	Erythropoiesis-stimulating agents
FDA	Food and Drug Administration
FFPE	Formalin-fixed and paraffin-embedded
GCP	Good Clinical Practice
GDPR	General Data Protection Regulation
GFR	Glomerular filtration rate
GGT	Gamma-glutamyl transferase
HAV	Hepatitis A virus
HBsAg	Hepatitis B surface antigen
HBV	Hepatitis B virus
HCV	Hepatitis C virus
HIV	Human immunodeficiency virus
HNSqCC	Head and neck region
HPV	Human papillomavirus
IB	Investigator's Brochure
ICF	Informed Consent Form
ICH	International Conference on Harmonization
ICI	Immune checkpoint inhibitor
IFN	Interferon
IMP	Investigational medicinal product
INR	International Normalized Ratio
irAE	Immune-related adverse event
IRB	Institutional Review Board
irRECIST	Immune-related RECIST
ITT	Intention-to-treat
mAb	Monoclonal antibody

Definition	Abbreviation
MMR	Mismatch repair
MTD	Maximum tolerated dose

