1.8 Study Rationale

Currently, patients with patients with PSqCCs presenting with advanced disease continue to present poor prognosis and OS of <1 year. Best supportive care remains an option for advanced in this setting and consideration of clinical trial is strongly recommended by the NCCN panel of experts.

The majority of primary PSqCC tumors express PD-L1. On the other hand, in a recent study it has been showed that PSqCC presents an identical genotype compared to other HPV-related SqCC tumors and very similar to squamous NSCLC. These data provide a rational basis for further investigation of anti-PD-1 and anti-PD-L1 immunotherapeutic in patients with advanced PSqCC. Of the patients who do respond, many can have long-term survival and therefore there is much interest in identifying these patients using prognostic and predictive biomarkers.

For HPV-related cancers, the role of HPV as molecular marker ICIs-based therapy is quite scarce and not conclusive and future clinical trials should include the HPV status in the evaluation of prognostic/predictive biomarkers.

Preliminary data with INCMGA00012 (retifanlimab) in ~200 patients have shown promising antitumor activity, resulting in response rates similar to those observed with other ICIs. However, no data are available so far with anti-PD-1 and anti-PD-L1 agents used in this tumor subtype. In order to determine if immunotherapy could benefit this population, this multicenter, open-label, phase II clinical trial will evaluate the efficacy and safety of the of anti-PD1 INCMGA00012 (retifanlimab) in patients with advanced PSqCC previously treated or not with chemotherapy. Unlike other currently ongoing studies, this trial will evaluate the activity of immunotherapy in a series of patients with advanced PSqCC regardless of their prior treatment and extension of the disease.

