3.2.4 Follow-up after treatment discontinuation

EoS will occur 12 months after the last patient has been enrolled in the study (treatment start).

Patients discontinuing the study treatment period will enter a post-treatment follow-up period during which survival and new anti-cancer therapy information will be collected every 3 months (\pm 14 days) from the last dose of investigational product until the end of study (EoS).

During this visit, status survival and post study anti-cancer therapy evaluation will be collected (telephone contact is acceptable).

LPLV: 12 months after first study dose of the last patient or progressive disease experienced in all patients or when the trial is terminated by the Sponsor, whichever is earlier.

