 - o When there is no evaluable tumor assessments best overall response will be NE.
- Unconfirmed Objective Response Rate (ORR) is defined as the proportion of patients with best overall response of unconfirmed CR or unconfirmed PR.
- Unconfirmed Clinical Benefit Rate (CBR) is defined as the proportion of patients with best overall response of unconfirmed CR or unconfirmed PR or SD ≥ 12 w.
- Confirmed Objective Response Rate (ORR) is defined as the proportion of patients with best overall response of confirmed CR or confirmed PR.
- Confirmed Clinical Benefit Rate (CBR) is defined as the proportion of patients with best overall response of confirmed CR or confirmed PR or SD ≥ 12 w.
- PFS is defined as the time from start dose until death by any cause or objective tumor progression according to RECIST v.1.1 or clinical disease progression. Patients with no progression or death will be censored at the date of their last evaluable imaging previous 35 days after last dose administration date. Censoring rules are specified below:

Situation	Date of progression or censoring	Outcome
Progression documented between scheduled visits	Earliest of: 
 • Date of assessment by investigator (if progression is based on clinical criteria); or • Date of assessment showing new lesion (if progression is based on new lesion); 	Progressed

Situation	Date of progression or censoring	Outcome
	or • Date of last radiological assessment of measured lesions (if progression is based on increase in sum of measured lesions).	
Death before first progression disease (PD) assessment	Date of death.	Progressed
Death between adequate assessment visits	Date of death.	Progressed
No progression	Date of last radiological assessment of measured lesions.	Censored
Treatment discontinuation for undocumented progression	Date of last radiological assessment of measured lesions.	Censored
Treatment discontinuation for toxicity or other reason	Date of last radiological assessment of measured lesions.	Censored

- 6-months PFS rate is defined as the proportion of patients who are alive and progression-free at 6 months from the date of first dose of study treatment based on RECIST criteria.
- The Overall Survival (OS) is defined as the time from start dose until death from any cause. Patients with no death will be censored on the last available follow-up date.

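### Follow-up time in SAP 5.2 does not separate death from censoring, so its plain median understates how long patients were followed for survival

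*SAP*

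**What the plan says.** SAP 5.2 (Subject Disposition) lists follow-up time among its descriptive items and gives it as "defined as the time from start dose until the last available follow-up date". It does not restrict the item to survivors and does not say what happens to a patient who has died.

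The default summary for such a variable, which applies where no other is specified, is in SAP 5.1: "Continuous data will be summarized in terms of the number of observations, mean, standard deviation (SD), median, minimum, maximum, and first and third quartiles". No other is specified for follow-up time. SAP 5.1 reserves Kaplan-Meier for time-to-event functions ("The Kaplan-Meier method will be used to estimate the time to event function, the median of time to event"). The protocol does not define follow-up time.

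SAP 5.4.1.1 uses the same date in the OS definition: "Patients with no death will be censored on the last available follow-up date".

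On timing, the Protocol synopsis gives recruitment as "Estimated at least 12 months in order to enroll 18 patients". Protocol 3.2.4 says "EoS will occur 12 months after the last patient has been enrolled in the study (treatment start", with Appendix 1 in agreement. The same section lets the last visit fall earlier, if all patients have progressed or the sponsor stops the trial. The schedule in SAP 1.5 instead places end of study 12 months after the last study dose.

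**The concern.** Nobody is followed after death, so the natural reading is that a dead patient's last available date is his date of death. A living patient's is his OS censoring date. The variable is then the observed OS time with the death indicator removed.

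A median of that variable cannot distinguish a completely followed cohort with early deaths from a poorly followed one. Readers need the distinction. SAP Table 2 promises 1- and 2-year OS rates, and SAP 5.4.5 relies on drop-out being unrelated to prognosis. A follow-up figure that falls as mortality rises makes well-followed data look immature.

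**Working it through.** The plan states no expected follow-up figure, so there is none to reproduce. The check is how far the SAP 5.2 median would lie from the median potential follow-up.

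**Inputs from the documents.** Accrual of at least 12 months (Protocol synopsis); end of study 12 months after the last patient starts (Protocol 3.2.4); 18 patients.

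**Assumptions.** Uniform accrual over A = 12 months, no loss to follow-up, and exponential OS with median m. The documents give no expected OS on treatment. Protocol 1.8 says current patients "continue to present poor prognosis and OS of <1 year", and Protocol 1.1 gives a 5-year OS rate below 50% for stage IV disease, which bounds the median only at 60 months. I therefore take m from 6 to 12 months, with 24 and 60 months for contrast.

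**Potential follow-up.** C is uniform on 12 to 24 months, so its median is 12 + 12/2 = 18 months.

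**Median under SAP 5.2.** The observed time is min(T, C), whose survivor function is the product of those of T and C.
- Up to 12 months nobody is administratively censored, so the product is the OS curve itself. If median OS is 12 months or less, the median follow-up equals median OS, whatever the shape of the OS curve.
- Beyond 12 months, solve exp(−λt) × (24 − t)/12 = 0.5 with λ = ln 2/m. For m = 24, t = 14.8: 0.652 × 0.767 = 0.50. For m = 60, t = 16.7: 0.825 × 0.608 = 0.50.

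**Share dead by end of study.** 1 − [exp(−12λ) − exp(−24λ)]/(12λ).

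| Median OS (months) | Median under SAP 5.2 (months) | Divided by 18 | Dead by end of study |
|---|---|---|---|
| 6 | 6.0 | 33% | 86% |
| 9 | 9.0 | 50% | 74% |
| 12 | 12.0 | 67% | 64% |
| 24 | 14.8 | 82% | 40% |
| 60 | 16.7 | 93% | 19% |

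**Longer accrual.** With A = 18 months the median potential follow-up is 12 + 9 = 21 months, and median OS of 6 to 12 months gives 6/21 = 29% to 12/21 = 57%. With A = 24 months it is 12 + 12 = 24 months, and the range is 6/24 = 25% to 12/24 = 50%.

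**Simulation at n = 18 (5,000 trials per row, 12-month accrual).**

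| Median OS (months) | Mean of SAP 5.2 medians | Mean of reverse Kaplan-Meier medians | Reverse median not reached |
|---|---|---|---|
| 6 | 6.3 | 17.4 | 14.2% |
| 9 | 9.1 | 17.9 | 2.5% |
| 12 | 11.3 | 18.0 | 0.4% |

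The reverse Kaplan-Meier means are over the trials in which that median was reached. It recovers roughly 18 months, although with very high mortality it sometimes has no median.

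**The case against.** Observed time on study is a legitimate descriptive quantity, openly defined, and for living patients it is true follow-up. SAP 5.2 says no statistical tests are planned on it. The same list reports the database cut-off and the first-dose dates of the first and last patients, which bound the potential follow-up. Event counts, Kaplan-Meier plots and swimmer plots also show maturity. All of this stands, and it limits the point to one of reporting. Those dates do not, however, give the median potential follow-up or show losses.

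A reader might infer three stronger things that the documents do not support.
- **That the figure would be about half the true value.** This holds only near a median OS of 9 months with 12-month accrual, or 12 months with 24-month accrual.
- **That the protocol expects OS under a year in this trial.** Protocol 1.8 describes current patients as part of the rationale, and adds that many responders can have long survival.
- **That every patient has at least 12 months of potential follow-up.** The earlier last-visit option in Protocol 3.2.4 and the different end of study in SAP 1.5 leave that unsettled, and the plan itself allows 10% drop-out.

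That follow-up stops at death is also an inference, since the SAP is silent. It is the natural reading, and nothing in either document corrects it.

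Last, a reverse Kaplan-Meier median on OS says nothing about imaging follow-up. SAP Table 2 censors PFS and DoR at the last evaluable imaging up to 35 days after the last dose. Using the OS figure for those endpoints could make them look more mature than they are. This objection stands and shapes the fix.

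**Conclusion.** The point holds as a minor reporting weakness. As defined, the follow-up median treats early death and early loss alike, and it falls to median OS whenever that is shorter than every patient's potential follow-up. It is too strong to say the variable reports survival instead of follow-up, because it mixes the two.

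The understatement is large if survival is short (33% to 67% of 18 months for median OS of 6 to 12 months) and modest if it is long (82% to 93% for 24 to 60 months). These figures rest on 12-month uniform accrual, exponential OS, no loss to follow-up, and the Protocol 3.2.4 end of study at 12 months after the last start. None of the trial's inference depends on the item: ORR, the exact test, the sample size and the Kaplan-Meier estimates of OS, PFS and DoR are unchanged.

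**What to change.** In SAP 5.2, add: *Median follow-up for OS will be estimated by the reverse Kaplan-Meier method (alive at last contact = event, death = censored).* Keep the existing variable beside it, relabelled *observed time on study*, and state that it ends at death. If few patients survive, the reverse median may not be reached, so also give the minimum and maximum time from first dose to data cut-off.

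State that this figure describes OS follow-up only and is not the maturity measure for PFS or DoR.

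Reconcile the end-of-study definitions in Protocol 3.2.4 (with Appendix 1) and SAP 1.5, since they determine the potential follow-up.

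The cost is a sentence or two in the SAP and one further procedure call on the existing OS dataset, with no new data and no change to any decision rule. The small downside is an extra output and two follow-up figures that must be clearly labelled.

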5.3 Baseline Characteristics

Baseline characteristics will be provided for the FAS and PP set.

Descriptive statistics, including number of subjects, mean, standard deviation (SD), median and range for continuous variables and frequency and percent for categorical variables will be provided.

Baseline Characteristics:

- Demographics
- Vital Signs
- Toxic background
- Oncological history
- General Medical History
- Prior concomitant medication
- History of Penile Cancer
- Previous surgeries for penile cancer
- Previous early/advanced disease treatment for penile cancer
- HR status
- Penile cancer stage
- Viral Serology and TST
- Urinalysis
- Physical examination
- ECOG
- 12-Lead ECG

No statistical tests are planned for these data.

A by-subject listing of all demographic and other baseline characteristics will be provided.

